4.4.1 Primary Efficacy Endpoint

The primary endpoint, DFS, is defined as the time from randomization until the date of the first local, regional, or distant melanoma recurrence, occurrence of new primary melanoma, or death from any cause. The DFS component of melanoma recurrence will be assessed by the investigator. The DFS component of an occurrence of a new primary melanoma will be based upon the diagnosis made by a Roche-designated central pathology laboratory. For patients without a DFS event at the time of data cutoff, data will be censored at the date of the last disease assessment. For patients who are treated with any non-protocol anti-cancer therapy (defined as systemic therapy or radiation therapy) without a DFS event, the data will be censored at the date of the last disease assessment. For patients without a DFS event for whom no post-randomization disease assessment is available, the data will be censored on the randomization date.

For patients whose recurrence has been proven histologically, the date of melanoma recurrence will be defined as the earliest date of the scan or clinical examination that prompted the biopsy. For patients whose suspicious lesions were deemed not amenable to biopsy (see Protocol Section 4.5.1.4) or for patients who refuse a biopsy, the date of melanoma recurrence will be defined as the earliest date of the scan or clinical examination that would have prompted a biopsy. For patients with an occurrence of a new primary melanoma, the date of the new primary melanoma will be defined as the earliest date of the clinical examination or scan that prompted the biopsy.

The duration of DFS will be calculated as the earliest DFS event date or censoring date minus the randomization date plus 1 day, converted to months.

The final analysis of the primary endpoint of DFS will take place when approximately 120 DFS events have occurred for Cohort 1 and approximately 105 DFS events have occurred for Cohort 2 (see Section 2.3). The final DFS analyses for both cohorts will be conducted at the same time by using the dataset from the same data cutoff date for both cohorts. The primary efficacy analyses will be comparisons of the two treatment groups, using a two-sided,

stratified log-rank test for Cohort 1 and Cohort 2 separately. The statistical significance of the two DFS tests is defined by the rule outlined below.

The hierarchical testing procedure, whereby Cohort 2 is tested first, will be used to adjust for comparison of two treatment groups (vemurafenib vs. control) for the two cohorts, in order to maintain an overall Type I error rate of 0.05 (two sided) for the final analysis of the primary endpoint of DFS. If the p-value for Cohort 2 is ≤ 0.05 , i.e., the vemurafenib treatment group is statistically significantly different from the control group in Cohort 2, then, Cohort 1 will be tested. If the p-value for Cohort 1 is ≤ 0.05 , then the vemurafenib treatment group is also statistically significantly different from the control group in Cohort 1. That is:

- Step 1: If $p_2 \leq 0.05$, then vemurafenib treatment group is statistically significantly different from the control group in Cohort 2. Go to step 2.
- Step 2: If $p_1 \leq 0.05$, then vemurafenib treatment group is also statistically significantly different from the control group in Cohort 1.

p_1 and p_2 are the p-values of final DFS analyses in Cohort 1 and Cohort 2, respectively.

Median DFS time will be estimated using the Kaplan–Meier method, and the two-sided 95% CI will be calculated using the method of Brookmeyer and Crowley (1982) for each cohort. In addition, Kaplan-Meier methodology will be used to estimate landmark (e.g., 1-year, 2-year, and 3-year) DFS rates and the associated two-sided 95% CIs for each treatment arm, and the Kaplan-Meier curves will be provided. The HR for DFS (recurrence, new primary melanoma, or death) and the associated two-sided 95% CI will be computed using a stratified Cox proportional hazards model.

The stratification factors in the stratified analyses are the stratification factors used in randomization of patients in each cohort. For Cohort 1, stratified analyses will incorporate two stratification factors: pathologic stage (Stage IIC, Stage IIIA, and Stage IIIB) and region (North America, Australia/New Zealand/South Africa/Latin America, rest of the world). For Cohort 2, stratified analyses will incorporate one stratification factor, region (North America, Australia/New Zealand/South Africa/Latin America, rest of the world).

As a sensitivity analysis, an unstratified log-rank test will be performed and the unstratified HR will be provided for each cohort.

In addition, the following sensitivity analyses will be performed for DFS by study cohort:

- Missing assessments for patients later diagnosed with a DFS event: For patients with a DFS event (other than death) who missed two or more scheduled assessments immediately prior to the event, the date of the event will be replaced by the date of the last disease assessment, plus 1 day. For patients whose DFS event was death and who died after missing two or more scheduled assessments, data will be censored at the date of the last disease assessment.
- Off-schedule assessments with a DFS event: For patients with a DFS event at an off-schedule visit, the date of event will be replaced by the date of the next scheduled disease-assessment visit.

As an exploratory analysis, DFS analyses based on the pooled data from both cohorts will also be performed for descriptive purposes to characterize the benefit of vemurafenib in the total study population. This exploratory analysis will be stratified by region.

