Protocol GO27826 has been amended as a result of the primary analysis of efficacy and safety (data cutoff 17 April 2017) and an analysis of secondary malignancies (data cutoff 3 July 2017; approximately 94 weeks after the last patient started study treatment). The study did not meet its primary endpoint. A statistically meaningful disease-free survival benefit for vemurafenib treatment was not demonstrated in Cohort 2, as required by hierarchical testing defined in the Statistical Analysis Plan. Safety analysis showed that patients treated in this study had a safety profile consistent with that of patients treated with vemurafenib for unresectable or metastatic melanoma with *BRAF*^{V600} mutation, an approved indication. The analysis of secondary malignancies demonstrated that overall incidences of cutaneous squamous cell carcinoma (including keratoacanthoma) among the vemurafenib-treated patients in this study was similar to the incidence reported in vemurafenib-treated patients with unresectable or metastatic melanoma with *BRAF*^{V600} mutation across studies: approximately 20%.

Changes to the protocol are summarized below:

- The end of study definition has been refined (see Sections 3.2, 6.4, 6.9, and Appendix 1), the length of patient follow-up has been reduced (see Sections 3.1, 3.2, 4.4.2, 4.5, 4.6, 5.1, 5.3, 5.4, 5.5, and Appendix 1), and in patients who had polyp(s) found at the 3-month post-treatment colonoscopy, a further colonoscopy after an additional 3 years is not required (see Sections 4.5, 5.1, and Appendix 1). The last patient in the treatment phase took their last dose of study medication on 14 September 2016. The reduction in the length of follow-up and earlier closure of the study is based on the following considerations:

The primary endpoint was not met; therefore, long-term overall survival data are no longer required, as registration plans are no longer being pursued.

No new safety signals were identified in the primary analysis; therefore, there is no need for additional safety monitoring.

An extensive safety database exists for vemurafenib, with more than 6,200 patients having been treated in company-sponsored clinical trials and a cumulative market exposure to vemurafenib of more than 45,016 patients.

- The reporting of the term “sudden death” has been updated to also require the presumed cause of death (Section 5.3.5.7).
- Event reporting for hospitalization has been clarified (Section 5.3.5.9).

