3.3.2 Rationale for Patient Population

This study includes patients with AJCC v7 Stages IIC, IIIA (patients with at least one nodal metastasis > 1 mm in diameter), IIIB, and IIIC melanoma, primarily because the risk of melanoma recurrence is in excess of 50% over the 5-year period after primary surgical resection and 5-year OS estimates vary from 40% to 60% in these patients (Balch et al. 2009). This segment of the melanoma patient population has a high unmet medical need for effective adjuvant treatment.

On the basis of historical data, the median recurrence-free interval in patients with Stages IIC–IIIB disease is expected to be approximately 24 months, on average. In contrast, the median recurrence-free interval for Stage IIIC patients is expected to be a much shorter 7.7 months (Eggermont et al. 2008; Eggermont AM, "Update on staging, tumor burden and adjuvant therapy," presented at Perspectives in Melanoma XIV Conference, Sept 17–18, 2010). Because of the disparate distributions of time to melanoma recurrence for the different substages and in order to ensure adequate power to detect the hypothesized treatment effect across a broad spectrum of patients at high risk for recurrence, eligible patients will be grouped into two independently powered cohorts: Stage IIC–IIIB patients will be in Cohort 1 and Stage IIIC patients will be in Cohort 2.

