2.3 SAMPLE SIZE AND ANALYSIS TIMING

The final primary efficacy endpoint (DFS) analyses for the two cohorts will be conducted according to the procedure specified in Section 4.4.1.

2.3.1 Cohort 1

The final analysis of the primary endpoint of DFS for Cohort 1 will take place when approximately 120 DFS events have occurred, on the basis of the following assumptions:

- Two-sided, stratified log-rank test at the 0.05 significance level

- 80% power
- Median DFS for the control arm of 24 months and estimated median DFS in the vemurafenib treatment arm of 40 months (which corresponds to a hazard ratio [HR] of 0.60)
- 5% annual loss to follow-up for DFS
- No interim analysis

Assuming an accrual rate of 8 patients per month in Cohort 1 and a 17-month ramp-up period to reach steady-state enrollment, approximately 300 patients will be required to be enrolled in Cohort 1 during 43 months and followed for an additional 7 months in order to observe 120 DFS events.

On the basis of the assumptions above, 120 DFS events are projected to occur in Cohort 1 approximately 50 months after the first patient is randomized in this study. At that time, it is projected that median follow-up time will be 21 months in Cohort 1, and the minimum follow-up time (e.g., for the last patient randomized) is projected to be 7 months. Also on the basis of the assumptions of 120 DFS events required and a target HR of 0.60, it is projected that an observed HR of 0.70 or better in the DFS analysis will result in a statistically significant difference between treatment arms (i.e., HR of 0.70 is the minimally detectable difference for that analysis).

A summary of the assumptions and characteristics of the DFS analysis for Cohort 1 is shown in [Table 1](#).

For Cohort 1, on the basis of the assumptions of a target HR of 0.60, 120 DFS events would provide 80% power to detect a 16% absolute increase in the 2-year DFS rate (50% vs. 66%, corresponding to a 40% risk reduction; i.e., HR of 0.60).

2.3.2 Cohort 2

The final analysis of the primary endpoint of DFS for Cohort 2 will take place when approximately 105 DFS events have occurred, on the basis of the following assumptions:

- Two-sided, stratified log-rank test at the 0.05 significance level
- 80% power
- Median DFS for the control arm of 7.7 months and estimated median DFS in the vemurafenib treatment arm of 13.3 months (which corresponds to an HR of 0.58)
- 5% annual loss to follow-up for DFS
- No interim analysis

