Assuming an accrual rate of 5 patients per month in Cohort 2 and a 27-month ramp-up period to reach steady-state enrollment, approximately 175 patients will be required to be enrolled in Cohort 2 over 40 months in order to observe 105 DFS events.

A summary of the assumptions and characteristics of the DFS analysis for Cohort 2 is shown in [Table 1](#).

For Cohort 2, on the basis of the assumptions of a target HR of 0.58, 105 DFS events would provide 80% power to detect a 17% absolute increase in the 2-year DFS rate (12% vs. 29%, corresponding to a 42% risk reduction; i.e., HR of 0.58).

Table 1 Assumptions and Characteristics for Disease-Free Survival Analyses by Cohort

	Cohort 1	Cohort 2
Patients enrolled	300	175
Hazard ratio targeted	0.60	0.58
Target median (control)	24 months	7.7 months
Target median (vemurafenib)	40 months	13.3 months
Final DFS analysis		
Number of DFS events	120	105
MDD hazard ratio ^a	0.70	0.68
α level (two sided)	0.05	0.05
Power	80%	80%

DFS=disease-free survival; FPI=first patient in; MDD=minimum detectable difference.

Note: A 5% annual dropout rate is anticipated for DFS analyses.

^a Minimally detectable difference; the largest observed hazard ratio that is projected to be statistically significant.

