3. STUDY CONDUCT

3.1 RANDOMIZATION ISSUES

After written informed consent has been obtained and eligibility has been established, each patient will be assigned an identification number and randomized to one of the two treatment arms with the use of an interactive voice or Web response system (IxRS). As noted in Section 2, randomization will be stratified by pathologic stage (Stage IIC, Stage IIIA, Stage IIIB) and region (North America, Australia/New Zealand/South Africa/Latin America, rest of the world) in Cohort 1 and by region (North America, Australia/New Zealand/South Africa/Latin America, rest of the world) in Cohort 2. A stratified, permuted, block randomization scheme will be used to obtain approximately a 1:1 allocation between the two treatment groups.

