4.4 EFFICACY ANALYSIS

Unless otherwise specified, all efficacy analyses will be performed on the ITT population. The primary and all secondary objectives of this study will be evaluated separately for each cohort.

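### The exploratory pooled DFS analysis stratifies by region but not stage, so its hazard ratio can fall outside both cohort hazard ratios; a post hoc stage-stratified supplement is a cheap improvement

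*SAP*

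**What the plan says.** SAP 4.4.1 and Protocol 6.4.1 both add an exploratory, descriptive DFS analysis of the pooled cohorts, and both state: "This exploratory analysis will be stratified by region". Neither names cohort or stage as a stratum for it.

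The surrounding text treats stage as important:

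- SAP 3.1, on Cohort 1: "randomization will be stratified by pathologic stage (Stage IIC, Stage IIIA, Stage IIIB) and region". Cohort 2 is Stage IIIC only and is randomized within region.
- SAP 4.4.1, on the analyses within each cohort: "The stratification factors in the stratified analyses are the stratification factors used in randomization of patients in each cohort". The Cohort 1 HR is therefore stratified by stage and region, and the Cohort 2 HR by region.
- Protocol 3.3.2 gives the reason for two cohorts: "Because of the disparate distributions of time to melanoma recurrence for the different substages".
- SAP 4.4: "The primary and all secondary objectives of this study will be evaluated separately for each cohort". Two cohort HRs will therefore stand beside the pooled one.

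**The concern.** The pooled analysis leaves out the factor on which the trial was divided. Within a region, a Stage IIIC patient and a Stage IIC to IIIB patient sit in the same risk set, although their planned control hazards differ about threefold (24 / 7.7 = 3.1). Two things follow.

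- High-risk patients leave the risk set earlier, and they leave faster on placebo than on vemurafenib. The arms drift apart in case mix over time, and a common treatment effect is pulled toward 1.
- Randomization balances the arms within stage, but the model ignores this, so its standard error is larger than the real sampling variation.

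What is at stake is how a descriptive summary reads. A total-population HR weaker than the HR in each of its two parts is hard to explain and does not serve the purpose of the analysis.

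**Working it through.** **Plan's own figures.** The Schoenfeld formula is events = 4(1.960 + 0.842)² / (ln HR)².

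- HR 0.60 needs 121 events, and power at 120 is 79.9%.
- HR 0.58 needs 106 events, and power at 105 is 79.7%.
- The largest significant HR is exp(−1.96 × 2/√events): 0.699 at 120 events and 0.682 at 105.

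These match SAP 2.3 and SAP Table 1. The documents state no pooled HR.

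**Inputs from SAP 2.3.** There are 300 patients (control median 24 months, HR 0.60) and 175 patients (7.7 months, HR 0.58), allocated 1:1, with 5% annual dropout. Accrual follows "an accrual rate of 8 patients per month in Cohort 1 and a 17-month ramp-up period" to 43 months and "an accrual rate of 5 patients per month in Cohort 2 and a 27-month ramp-up period" to 40 months. SAP 4.4.1 requires one data cutoff for both cohorts; Month 50 is the SAP's projection.

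**Assumptions not in the documents.** Exponential DFS, linear ramp-up, three equal regions, Cohort 1 stage mix 10/30/60%, and blocks of 4.

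**Expected pooled HR.** The model gives 117 and 130 events at Month 50. With no risk set shared between cohorts, the pooled log HR is close to an event-weighted mean: (117 × ln 0.60 + 130 × ln 0.58)/247 = −0.529, so HR 0.589. Solving the Cox score equation numerically with the cohorts sharing risk sets gives 0.627. Simulation of 20,000 trials of planned size gives 0.626 with region only and 0.589 with region and stage. The shift is ln(0.626/0.589) = 0.061, which is 0.47 of the model standard error of 0.1297.

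**Other cohort effects** (10,000 trials per row, 20,000 for the first):

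| True HR, Cohort 1 / Cohort 2 | Region only | Region + stage | Shift in SE | Region-only HR outside both cohort HRs |
|---|---|---|---|---|
| 0.60 / 0.58 | 0.626 | 0.589 | +0.47 | 33.7% |
| 0.70 / 0.70 | 0.728 | 0.699 | +0.33 | 26.7% |
| 0.60 / 0.80 | 0.713 | 0.701 | +0.14 | 16.1% |
| 0.60 / 0.90 | 0.746 | 0.750 | −0.04 | 8.8% |
| 0.60 / 1.00 | 0.776 | 0.797 | −0.21 | 3.8% |
| 1.00 / 0.60 | 0.834 | 0.782 | +0.52 | 2.7% |

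With region and stage strata the share outside is 0.0% in every row. With region and cohort strata it is 6.0% in the first row.

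**Why region and stage strata give a guarantee.** No stratum then contains patients from both cohorts, so the pooled score is U(b) = U1(b) + U2(b). Each part decreases in b and is zero at its own cohort estimate, so the sum is zero between the two. Region and cohort strata lack this property, because the Cohort 1 part would be stratified by region alone while the reported Cohort 1 HR is stratified by stage as well.

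**Calibration.** At the planned HRs, region only has model SE 0.130 and empirical SD 0.120; region and stage have 0.132 and 0.133. With no treatment effect (20,000 trials), a nominal 5% test rejects in 3.3% with region only and 5.2% with region and stage.

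**Sensitivity of the region-only result at the planned HRs:**

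- Cutoff from 44 to 60 months: 0.622 to 0.634.
- Uniform accrual: 0.631.
- Region mix differing between cohorts: 0.624 (moderate) and 0.614 (strong).
- Stage medians differing within Cohort 1 (22.2 and 18.7 months from Protocol Table 1, IIIA assumed 24 to 48): 0.622 to 0.636.
- Weibull shape 0.8: about 0.61, with about 22% outside both.
- Weibull shape 1.2: about 0.64, with about 48% outside both.

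The region-and-stage HR stays at about 0.59.

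**The case against.** The strongest objection is that this is a choice of estimand. For a summary of the total population, a less conditional HR is legitimate, and hazard ratios are non-collapsible: even with perfect balance, an HR that ignores a strong prognostic factor need not equal the HRs within its levels. This stands in part. The documents do not say whether the pooled HR is meant to be conditional or marginal. It does not explain away the oversized standard error, and a less conditional HR cannot be compared directly with the stage-stratified Cohort 1 HR beside it.

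Second, the practical effect is small. When the region-only HR is weaker than both cohort HRs at the planned effects, it exceeds the weaker one by a median of 3.4% (90th percentile 8.4%). The 95% limits lie about 29% either side (exp(1.96 × 0.13) = 1.29). This stands: nobody would be misled about whether there is benefit.

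Third, near-equal effects may not be the relevant case. The rationale for Protocol Version 10 reports: "A statistically meaningful disease-free survival benefit for vemurafenib treatment was not demonstrated in Cohort 2". This also stands, and it is why the unequal rows belong beside the planned one. It does not establish what the true Cohort 2 effect is.

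A reader might infer that the SAP breaks its own stratification rule. It does not: that sentence concerns the analyses within each cohort, and both documents agree on region for the pooled one. A reader might also infer that the pooled result is always diluted. It is not: at 0.60 / 1.00 the region-only HR is the more favourable of the two.

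**Conclusion.** The point holds as a modest, cheap improvement. Stratifying by region alone puts patients with a threefold planned hazard difference into shared risk sets. At the planned HRs this moves the pooled HR from 0.59 to about 0.63 (about 0.61 to 0.64 over DFS shape, accrual shape, cutoff and region mix). The pooled HR then lies outside both cohort HRs in about a third of trials, roughly 20% to 50% depending on DFS shape. If Cohort 2 benefits less, the shift nearly vanishes or reverses: about 0.71 against 0.70 at 0.60 / 0.80 (16% outside), and about 0.78 against 0.80 at 0.60 / 1.00 (4% outside). The region-only standard error is about 8% too large (0.130/0.120 = 1.08).

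The sizes rest on the planning assumptions and on the added ones listed with the calculation. The guarantee for region and stage strata rests on none of them. When the cohort effects differ, any pooled HR remains only a weighted average.

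It would be too strong to say that a conclusion of the trial is affected. The analysis is descriptive, carries no alpha and sits outside the testing hierarchy. Nor do the documents give the observed pooled HR, so they cannot show that it was distorted.

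**What to change.** Keep the region-only sentence in SAP 4.4.1 and Protocol 6.4.1, and keep its result in the report. SAP Version 4 (17 March 2017) predates the 17 April 2017 data cutoff, so that analysis is the pre-specified one and should not be rewritten after the primary analysis.

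Add one supplementary pooled DFS log-rank test and Cox model stratified by region and stage (IIC, IIIA, IIIB, IIIC, where IIIC is Cohort 2). Label it post hoc and show it beside the region-only result and the two cohort HRs. Region plus cohort would remove most of the shift but leave the pooled HR outside both cohort HRs in about 6% to 7% of trials at the planned effects, so four-level stage is preferable.

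The cost is one extra output and no new data. Three regions by four stages make twelve strata, workable with about 247 projected events (117 + 130). The model standard error rises slightly, from 0.130 to 0.132, so the interval does not narrow; its width then matches the actual sampling variation.

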4.4.2 Secondary Efficacy Endpoints

4.4.2.1 Distant Metastasis–Free Survival

DMFS is defined as the time from randomization until the date of diagnosis of distant (i.e., non-locoregional) metastasis or death from any cause. For patients without a DMFS event at the time of data cutoff, the data will be censored at the date of the last disease assessment. If no post-randomization disease assessment is available, the observation will be censored on the randomization date.

DMFS will be analyzed at the time of the final DFS analysis in each cohort. The analysis methods to be employed for DMFS are the same as those described for the primary endpoint of DFS.

